## 17.4.7.1. Derivation

The post-extubation NIV respiratory support details can be found on the Post Mechanical Ventilation follow up CRF. The start point for the duration of post-extubation respiratory support will the date and time of final successful extubation as described in section 17.4.1.1, if this has been observed.

The end point will be the final date and time (MACRO variable PMV02DTD) that NIV is ended as indicated by the final observation for which the MACRO variable PMVTOSPC (Type of Supplementary O2) = "NIV".

If NIV is stopped and then restarted this time will be included in the overall time of post-extubation respiratory support. If no NIV is recorded then time on post-extubation respiratory support will be assumed to be zero.

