# 5. Statement of Compliance

This Statistical Analysis Plan (SAP) provides a detailed and comprehensive description of the preplanned final analyses for the study "BESS". The planned statistical analyses described within this document are compliant with those specified in brief within the BESS protocol v3.0 (31/07/2019). These analyses will be performed by the trial statistician.

This study is carried out in accordance with the World Medical Association Declaration of Helsinki (1964) and the Tokyo (1975), Venice (1983), Hong Kong (1989) and South Africa (1996) amendments and will be conducted in compliance with the protocol, Liverpool Clinical Trials Centre (LCTC) Clinical Trials Unit (CTU) Standard Operating Procedures (SOPs) and EU Directive 2001/20/EC, transposed into UK law as the UK Statutory Instrument 2004 No 1031: Medicines for Human Use (Clinical Trials) Regulations 2004.

This study is a clinical trial of a medicinal product and is registered on the EudraCT database. This SAP has been developed to support the posting of results on the EudraCT system. This is a regulatory requirement which should be fulfilled within 6 months after the end of the study as defined within the clinical trial protocol. The results of the final analysis described within this SAP will be contained within a statistical analysis report. This report will be used as the basis of the primary research publications according to the study publication plan.

All analyses are performed with standard statistical software (SAS v9.4 or later) with the exception of the joint modelling analysis which will be performed using the JoineR package [5] package in R. The finalised analysis datasets, programs and outputs will be archived following Good Clinical Practice (GCP) guidelines and SOP GE012 Archiving procedures. The testing and validation of the statistical analysis programs will be performed following SOP ST001.

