#### 17. Efficacy Evaluations

#### 17.1. Data Sets Analysed

The principle of intention-to-treat, as far as practically possible, will be the main strategy of the analysis adopted for the primary outcome and all secondary outcomes. These analyses will be conducted on all randomised participants, in the group to which they were randomised, and for whom the outcome(s) of interest have been observed/measured. No imputations will be made.

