# 17.4.1.2. Analysis

Descriptive statistics will be presented split by treatment and overall for the time from randomisation to final successful extubation (before the data is transformed) and time off MV due to failed extubation. The summaries will be presented as median and interquartile range as the data is likely to be skewed.

A comparison of group means will be conducted using a two-sample t-test on the log transformed data (the log transformation will be done using natural logarithms). The between group difference of the log transformed data will then be back transformed by taking the exponent to give the geometric mean difference and the corresponding 95% confidence interval.

A linear mixed effects model will also be fitted on the log transformed data, using ANCOVA to test for a difference between groups with adjustment for the stratification factor of time on ventilation prior to randomisation (<24h and  $\geq$ 24h), sex and adjusted age at enrolment as a fixed effects and site as a random effect (random intercept only). The exponentiated between-group difference and corresponding 95% confidence interval will be reported.

The approach to the primary outcome analysis will be a compete case analysis and will only include those participants for which the primary endpoint has been observed. If there are any participants who have not recorded a successful extubation at the point at which they were last followed up (e.g. consent for follow up has been withdrawn) then sensitivity analysis will be conducted including these participants to assess the robustness of the primary outcome analysis.

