#### 17.4.5.1. Derivation

The post-extubation oxygen supplementation details can be found on the Post Mechanical Ventilation follow up CRF. The start point for the duration of post-extubation oxygen supplementation will the date and time of final successful extubation as described in section 17.4.1.1, if this has been observed.

The end point will be the final date and time (MACRO variable PMV02DTD) that any type of oxygen supplementation (NIV, high-flow  $O_2^2$  or low-flow  $O_2^3$ ) is ended as indicated by the final observation for which the MACRO variable PMVS02SC (Supplementary O2 stopped?) = "Yes".

If oxygen supplementation is stopped and then restarted this time will be included in the overall time of post-extubation respiratory support. If no oxygen supplementation is recorded then time on postextubation respiratory support will be assumed to be zero.

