# 17.4.7.2. Analysis

Descriptive statistics will be presented split by treatment and overall for the time from successful extubation to cessation of post-extubation respiratory support. The summaries will be presented as median and interquartile range as the data is likely to be skewed.

The comparative analysis will be as described in 17.4.1.2 but will just involve the two-sample t-test, a linear mixed effects model will not be used for this outcome.

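### Oxygen and NIV durations can be zero under the SAP but are compared on the log scale, and no rule is given for the zeros

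*SAP*

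**What the plan says.** Two secondary outcomes are durations measured from final successful extubation.

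- **Secondary Outcome 6, NIV (SAP 17.4.7.1):** "If no NIV is recorded then time on post-extubation respiratory support will be assumed to be zero". Only BiPAP and CPAP modes count as NIV here. High-flow and low-flow oxygen are separate categories in 17.4.5.1.
- **Secondary Outcome 4, any oxygen supplementation (SAP 17.4.5.1):** "If no oxygen supplementation is recorded then time on postextubation respiratory support will be assumed to be zero". This outcome counts NIV, high-flow and low-flow oxygen.

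The analysis sections 17.4.5.2 and 17.4.7.2 use the same sentence: "The comparative analysis will be as described in 17.4.1.2 but will just involve the two-sample t-test". The section they point to reads: "A comparison of group means will be conducted using a two-sample t-test on the log transformed data". It specifies natural logarithms and back-transformation to a geometric mean comparison. It has no other t-test.

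On the analysis set, SAP 17.1 says "These analyses will be conducted on all randomised participants, in the group to which they were randomised", provided the outcome was observed, and adds "No imputations will be made".

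Neither document gives an offset, a two-part model, a rank test or any other rule for a zero duration.

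**The concern.** The derivation creates a value that the analysis cannot use, so whoever programs the analysis has two ways out.

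1. **The logs become missing and the zeros are lost.** The comparison is then of duration among infants who needed support. Needing support arises after randomisation and treatment may affect it, so the randomised comparison is broken. If surfactant works by avoiding support altogether, this analysis cannot show it.
2. **A constant is added before taking logs.** The constant is not prespecified, and the estimated ratio depends heavily on it.

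Two named efficacy outcomes therefore lack an executable prespecified comparison, and the gap would be filled at the analysis stage.

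**Working it through.** **Inputs.** From protocol 11.3: 142 per arm, 284 in total, two-sided alpha 0.05. Assumed, because the documents give nothing on it: the share of zeros in each arm; non-zero durations log-normal with median 24 h and log-SD 0.8 or 0.9, identical in both arms.

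**The plan's own figure.** No calculation is given for these two outcomes. The only stated figure is the primary sample size, which reproduces. With v1 = ln(1 + 0.518²) = 0.237 and v2 = ln(1 + 0.613²) = 0.319, the log-mean shift is ln(0.845) − 0.5 × (0.319 − 0.237) = −0.209. Then n = (1.960 + 1.282)² × (v1 + v2) / 0.209² = 133.2 on unrounded inputs, so 134 per group. At 80% power the result is 99.5, so 100. Dropout: 134 / 0.95 = 141.05, so 142 per group and 284 overall.

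**Step 1: can the stated test be run?** ln(0) is minus infinity. A t-test on a sample that contains it returns no statistic and no p-value, so each zero must be removed or altered.

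**Step 2: if the zeros are lost.** Expected number lost = 142 × (p_control + p_treated). Rejection rates come from simulation and the ranges cover repeat runs.

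| Zeros, control v treated | Infants lost of 284 | Log t-test, zeros lost | Rank-sum test, zeros kept |
|---|---|---|---|
| 10% v 20% | 142 × 0.30 = 43 | 5-6% | 31-32% |
| 30% v 50% | 142 × 0.80 = 114 | 5-6% | 85-86% |
| 60% v 75% | 142 × 1.35 = 192 | 5-6% | 74-77% |

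The t-test column stays near the nominal 5% by construction, because users have the same durations in both arms. The whole treatment effect lies in the infants it has lost.

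**Step 3: reversal is possible.** Suppose 30% zeros in control, and suppose treatment spares the quarter of NIV users who would have had the shortest durations (log-SD 0.8). The mean of a standard normal above its lower quartile is 0.318 / 0.75 = 0.424. The ratio among remaining users is then exp(0.8 × 0.424) = 1.40, against treatment. In simulation the log t-test was significant in that wrong direction in 87% of runs. The rank test with zeros kept rejected in 24%, so it has limited power here.

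**Step 4: if a constant c is added.** With 30% v 50% zeros, the log ratio is about (0.50 − 0.30) × (ln c − ln 24), where ln 24 = 3.178.

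- c = 1 h: exp(0.2 × −3.178) = 0.53 (simulated 0.52)
- c = 0.1 h: exp(0.2 × −5.481) = 0.33 (simulated 0.33)
- c = 0.01 h: exp(0.2 × −7.783) = 0.21 (simulated 0.21)

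The same data give a 48% or a 79% reduction, depending only on the constant.

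**Step 5: which outcome is more exposed?** Any infant with NIV also counts as having oxygen support, so the zeros of Outcome 4 are a subset of those of Outcome 6. Outcome 4 has no more zeros, and possibly far fewer.

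**The case against.** **An untransformed t-test may have been meant.** The derivations of the primary outcome and of SBT readiness state the log step, and these two derivations do not. The summaries for the primary outcome, SBT readiness and length of stay are described as before transformation, and that phrase is absent for these two. This is a fair point, but the cross-reference leads only to a t-test on logs. If the raw scale was intended, the SAP still needs correcting.

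**The SAP does not plan to exclude the zeros.** A reader might infer a planned, silent deletion. The documents do not support that. SAP 17.1 points towards keeping every observed outcome, and SAP 18 says missing data will be quantified for all outcomes, so lost values would be visible in the report.

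**Zeros are not necessarily the best outcomes.** A reader might infer this too. For Outcome 6 it is wrong, because an infant extubated to high-flow or low-flow oxygen scores zero. Read literally, the rule could also give zero to an infant who dies on the ventilator. Protocol 10.2.3 puts mortality at 1-2%, or about 3 to 6 of 284 infants if all were scored this way. This objection stands and it shapes the fix.

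**The size is assumed.** The documents give no share of zeros, and the scenarios place all the benefit in avoiding support. That is why a range is shown, and no single row should be applied to both outcomes.

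**Conclusion.** The point holds. Zero is assigned, the comparison is on natural logarithms, and nothing connects the two. Infants extubated without NIV (including those on high-flow or low-flow oxygen only), or without any oxygen support, either drop out or enter through an unplanned constant.

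That conclusion rests on the SAP text alone. The size rests on assumed zero shares and identical log-normal durations among users. On those assumptions, a plan that loses the zeros has no power beyond its 5% error rate to detect a benefit that consists of avoiding support. If few infants have zero, which is more likely for oxygen than for NIV, the practical effect is small.

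It should be fixed, but it does not threaten the trial's main result. These are secondary outcomes, and the primary outcome, its models and the sample size are untouched.

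**What to change.** Amend the SAP before unblinded analysis, for Secondary Outcomes 4 and 6:

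1. **Do not log-transform.** The lead comparison is a Wilcoxon rank-sum test on all infants with the outcome observed, zeros included. It may be stratified by prior ventilation (<24h, ≥24h) only. Stratifying by site as well would give about 14 × 2 = 28 cells, or roughly 284 / 28 = 10 infants each, which is sparse.
2. **Supporting results.** Report the difference in mean hours with a bootstrap 95% confidence interval. Also report the relative risk of any NIV (Outcome 6) or of any oxygen support (Outcome 4). Protocol 11.5 already reports binary data as relative risks.
3. **Define who scores zero.** Assign zero only to infants with an observed successful extubation and no such support recorded afterwards. Infants who die or are withdrawn before extubation are then not scored as zero.

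The cost is SAP wording, with no new data. The small downside is that these two results are no longer geometric mean ratios like the other durations.

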# 17.4.7.2. Analysis

Descriptive statistics will be presented split by treatment and overall for the time from successful extubation to cessation of post-extubation respiratory support. The summaries will be presented as median and interquartile range as the data is likely to be skewed.

The comparative analysis will be as described in 17.4.1.2 but will just involve the two-sample t-test, a linear mixed effects model will not be used for this outcome.

# 17.4.8. Secondary Outcome 7: Duration of stay at PICU and in hospital

The outcome will assess if there is evidence of a difference in the duration of stay in PICU and in hospital between arms.

#### 17.4.8.1. Derivation

The duration of stay at PICU will be calculated by taking the difference between the date/ time of randomisation taken from the Almac randomisation log and the date/ time of discharge from PICU (PDAISDTD) on the PICU Discharge CRF or the date of death (DNBDIDD) Day 90 Status CRF if the death occurred before PICU discharge. This can be expressed as:

 $T(PICU) = \begin{cases} PDAISDTD, & if dicharged \\ DNBDIDD, & if death occurs in PICU - T_{RAND} \end{cases}$ 

The overall duration of stay in hospital (including both time in PICU and time in hospital) will be calculated by taking the difference between the date/ time of randomisation taken from the Almac randomisation log on and the date/ time of hospital discharge (PDA90DTD) on the PICU or the date of

<sup>4 If date and time of death is required to calculate time in hospital or time in PICU then this will be estimated at 12:00 as death is only recorded as date.

death (DNBDIDD) Day 90 Status CRF if death occurred before hospital discharge. This can be expressed as:

 $T(Hospital) = \begin{cases} PDA90DTD, & if dicharged \\ DNBDIDD, & if death occurs \end{cases} - T_{RAND}$ 

Note that if death occurs during PICU then T(Hospital) = 0.

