# 17.4.8.2. Analysis

Descriptive statistics will be presented split by treatment and overall for duration of PICU stay and hospital stay separately (before they have been transformed). The summaries will be presented as median and interquartile range as the data is likely to be skewed.

The comparative analysis will be as described in 17.4.1.2 for the duration of PICU stay and hospital stay, but will just involve the two-sample t-test, a linear mixed effects model will not be used for this outcome.

**17.4.9.** Secondary Outcome 8: Liverpool Respiratory Symptom Questionnaire The "Liverpool Respiratory Symptom Questionnaire" (LRSQ) score, a parent reported outcome measure of respiratory symptoms, at 6m (+/-1m) and 12m (+/-1m) [6]. The parents of infants randomised in season 3 will only complete the 6m questionnaire.

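### SAP 17.4.8.1 sets hospital stay to zero for a death in PICU, which contradicts its own formula and cannot be log-transformed

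*SAP*

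**What the plan says.** SAP 17.4.8.1 derives two stays, both starting at randomisation.

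- **Hospital stay** is the whole stay: "The overall duration of stay in hospital (including both time in PICU and time in hospital) will be calculated by taking the difference" between randomisation and hospital discharge, or the date of "death (DNBDIDD) Day 90 Status CRF if death occurred before hospital discharge". The displayed formula says the same. The note beneath it reads: "Note that if death occurs during PICU then T(Hospital) = 0".
- **PICU stay** ends at PICU discharge, or at the date of death taken from the "Day 90 Status CRF if the death occurred before PICU discharge".
- **Clock time of death:** a footnote says that, where a time is needed, "this will be estimated at 12:00 as death is only recorded as date".

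SAP 17.4.8.2 summarises both stays untransformed, by median and interquartile range. For the test, "The comparative analysis will be as described in 17.4.1.2 for the duration of PICU stay and hospital stay", without the mixed model. Section 17.4.1.2 specifies a "two-sample t-test on the log transformed data (the log transformation will be done using natural logarithms".

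SAP 17.1 puts every randomised infant with an observed outcome into the analysis, in the allocated arm, and rules out imputation.

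SAP 17.5.5.1 recognises a death in PICU by a blank PDA90DTD, which it labels PICU discharge. SAP 17.4.8.1 uses PDAISDTD for PICU discharge and PDA90DTD for hospital discharge.

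**The concern.** A stay that includes PICU time cannot be shorter than the PICU stay, yet the note makes it zero. A programmer has two incompatible instructions for the same infant. The independent programming in SAP section 21 covers the primary and safety analyses, so it would not expose the conflict.

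Under the note, the worst outcome takes the lowest possible value in the descriptive table and no value in the test. The comparison of hospital stay would then leave out infants whose time to death is known, contrary to SAP 17.1. SAP section 11 frames the trial as testing superiority in every outcome, so this comparison will be read as evidence of efficacy.

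**Working it through.** The plan gives no figure for this outcome. The one plan figure used is the total sample size in Protocol 11.3, which reproduces: 134 / 0.95 = 141.1, rounded up to 142 per arm, and 2 × 142 = 284.

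**1. The two rules on one infant.** Take randomisation on day 0 at 08:00 and a death in PICU dated day 5, set to 12:00.

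- T(PICU) = 5 × 24 + 4 = 124 h.
- T(Hospital) by the formula = 124 h; ln(124) = 4.82, which is usable.
- T(Hospital) by the note = 0 h; ln(0) is undefined (it tends to minus infinity), so there is nothing to enter in the t-test. The SAP gives no replacement rule.

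**2. How many infants.** Protocol 10.2.3 gives a likelihood of death of 1-2%, and Protocol 3.2 a PICU case-fatality of 1.75%. Assume that all deaths occur in PICU.

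| Mortality | Expected deaths, 284 infants | Per arm of 142 | Chance of at least one, 1 − (1 − p)^284 |
|---|---|---|---|
| 1% | 2.84 | 1.42 | 94.2% |
| 1.75% | 4.97 | 2.49 | 99.3% |
| 2% | 5.68 | 2.84 | 99.7% |

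At 1.75% in both arms (two independent binomials, n = 142), the arms differ by 2 or more deaths with probability 48%, and by 3 or more with probability 25%.

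**3. Effect on the summary.** Zero is the minimum possible value. Moving three values in an arm of 142 from above the median to zero lowers the median by three rank positions, so the median and quartiles change little.

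**4. PICU stay.** Death ends it at T(PICU), 124 h in the example. That is positive and stays in the test, although an early death reads as a short stay. The exception comes from the 12:00 convention. Randomisation on day 0 at 15:00 with a death dated day 0 gives 12:00 − 15:00 = −3 h, which has no logarithm.

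**5. The discharge variable.** Suppose an infant randomised on day 0 at 08:00 leaves PICU and dies on the ward on day 9. The formula gives T(Hospital) = 9 × 24 + 4 = 220 h. If PDA90DTD is hospital discharge, as in 17.4.8.1, it is blank for this infant. The 17.5.5.1 rule then classes the death as a PICU death, and the note turns 220 h into 0. If PDA90DTD is instead PICU discharge, as 17.5.5.1 labels it, the hospital stay in 17.4.8.1 would stop at PICU discharge for every infant discharged. One of the two labels must be wrong.

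**The case against.** The strongest reply is that the note is a slip. It would make sense if hospital stay had meant ward time after PICU, and the formula above it is clear. That may be so, but the documents do not say it, and the definition includes PICU time explicitly. The contradiction stands.

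It is also fair to say that little is affected: a secondary outcome, a few infants, and a median that hardly moves. Deaths are still compared by arm, with relative risks and 95% confidence intervals, in SAP 17.5.5 and 17.5.6, and SAP section 18 quantifies missing data for every outcome. A reader might infer that deaths vanish from the trial's results; they leave one secondary test only.

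A reader might also infer a large shift in favour of the arm with more deaths. With a typical stay of 240 h and zeros replaced by 0.5 h, five extra deaths in one arm give a geometric mean ratio of exp(−5 × ln(480)/142) = 0.80. Three extra deaths with zeros replaced by 1 h give exp(−3 × ln(240)/142) = 0.89. The arithmetic is right, but the plan does not lead there. The SAP contains no replacement constant and rules out imputation, and the 240 h stay is an assumption. About 3 to 6 deaths are expected in both arms together, and at equal 1.75% risk a difference of five or more has a probability of about 4%. Nor can these ratios be set against the 0.845 of Protocol 11.3, which is a ratio of arithmetic means (4.08/4.83) for ventilation time.

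Finally, ending a stay at death is a coherent definition of time spent in a unit. Preferring discharge alive is a choice of estimand, not the repair of an error. This part of the objection stands, and it is why the competing-event analysis belongs beside the planned one and should not replace it.

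**Conclusion.** The T(Hospital) = 0 note is wrong as written. It contradicts the definition and formula directly above it and yields a value that the planned test cannot use. The infants concerned, about 3 to 6 of 284, would rank as the shortest stays in the summary and be missing from the test. That count rests on the documents' 1-2% mortality and on all deaths occurring in PICU. It could be lower, since the trial excludes major congenital anomalies and clinical futility.

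The documents do not support the reading that death is the best score for PICU stay or is routinely deleted from it. There, death truncates a normally positive time, and only a same-day death after an afternoon randomisation gives an unusable value. Nor do they support a claim that the hospital-stay test is biased in a known direction. Deletion can move the ratio either way, depending on whether the deleted stays were short or long.

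The point should be settled before analysis, as a correction to a secondary outcome.

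**What to change.** 1. Delete the note in SAP 17.4.8.1. A death in PICU then has T(Hospital) equal to date of death minus randomisation, the same as T(PICU), and stays in the test. State what is done if the 12:00 convention gives a zero or negative stay.
2. Reconcile PDA90DTD and PDAISDTD between 17.4.8.1 and 17.5.5.1, so that ward deaths are not classed as PICU deaths and each stay ends at the intended discharge.
3. Keep the planned geometric mean comparison. Before allocation is known, add a supportive analysis for each stay: time from randomisation to discharge alive, with death as a competing event, reported as cumulative incidence by arm and a subdistribution hazard ratio with 95% confidence interval. Step 1 alone does not stop an early death from reading as a short stay.

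The cost is a SAP wording change, a check of two variable names against the CRF, and one extra analysis per stay outcome. The supportive analysis uses the dates already collected.
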